- any one of the following ≥ 6 months after surgery:
 1. a positive stress test, or
 2. self-reported stress-type UI symptoms (response of “sometimes” or “often” on the MESA questionnaire); or
 3. a positive pad test (≥ 15 ml leakage over 24 hours), or
 4. self-reported leakage by 3-day voiding diary.

Similarly, treatment failure specific to SUI is defined as:

- any surgical, pharmacological or behavioral retreatment for SUI at any point after the initial surgery for urine leakage; or
- any one of the following ≥ 6 months after surgery:
 1. a positive stress test, or
 2. self-reported stress-type UI symptoms (response of “sometimes” or “often” on the MESA questionnaire)

Once a woman is documented as a treatment failure, she cannot be classified as a success for that endpoint at later time points.

E. STUDY POPULATION

The study population will consist of women who have been diagnosed with predominant stress urinary incontinence (SUI).

E.1 Inclusion Criteria

1. Female
2. Predominant SUI as evidenced by:
 - Self-reported stress-type UI symptoms, of duration ≥ 3 months*
 - Mean micturition < 12 x/day
 - MESA stress symptom score (percent of total possible stress score) greater than MESA urge symptom score (percent of total possible urge score)
 - Observation of leakage by provocative Stress Test at a bladder volume ≤ 300 ml (Valsalva or cough-induced detrusor instability is considered mixed UI and therefore allowed.)
 - Maximum cystometric capacity ≥ 200 ml
 - Post-void residual (PVR) ≤ 150 cc by Stress Test or UDS with pelvic organ prolapse (POP) Stage I or lower. If POP is Stage II-IV, PVR > 150 cc is allowed.
 - Voiding not obstructed: maximum flow rate ≥ 12 ml/sec, PVR ≤ 150 cc, and detrusor pressure at maximum flow ≤ 50 cm H₂O. If POP Stage II-IV, maximum flow rate < 12 ml/sec, PVR > 150 cc, and/or detrusor pressure at maximum > 50 cm H₂O is allowed.
3. Urethral hypermobility as evidenced by resting angle $> 30^\circ$ or maximum straining angle $> 30^\circ$ on Q-Tip Test
4. Eligible for both Burch and sling procedures
 - No medical contraindications, e.g., current UTI, history of pelvic irradiation, history of lower urinary tract cancer
 - ASA class I, II, or III
 - No current intermittent catheterization
 - Candidate for harvesting of autologous rectus fascia graft
5. Available for 24-months of follow-up and able to complete study assessments, per clinician judgment.
6. Signed consent form

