Because the urge component of incontinence in women with mixed incontinence is not expected to be improved by either surgical procedure being studied, the requirement of negative self-report and negative pad test may prevent women from achieving the clinical endpoint of "overall treatment success" even if the surgery is successful in eliminating the stress component of incontinence. Therefore, although many reports of both Burch and sling procedures suggest "success" rates of approximately 80-85%, we expect to observe lower success rates in this trial, by approximately 15-20 percentage points. A sample size of 260 per group, or 520 total, would

ensure 80% power to detect a 12 percentage point difference (60% vs. 72%) using a two-sided $\alpha=.05$ Fisher's exact test. In order to meet the criteria for success, patients must be willing to undergo a fairly intensive measurement process (self-administered questionnaire, 3-day diary, 24-hour pad test, stress test). It seems likely that some women who consider themselves to be cured will not comply with this regimen. Therefore, to adjust for a 20% non-compliance rate, the target sample size will be inflated to 325 per group, or 650 total.

For the more mechanistic endpoint, “treatment success specific to SUI,” we assume a higher success rate, i.e., >80%. The target sample size will ensure >85% power for detecting a 10 percentage point difference (80% vs. 90%).

K.2 Interim Monitoring

Ordinarily, early stopping rules are based on monitoring the primary endpoints for a treatment difference so large that it is unethical to continue treating one group of patients with the “inferior” treatment, and on monitoring the treatments for safety. In this trial, however, several considerations argue against the usual motivations for early stopping procedures.

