Fisher's exact test will be used for unadjusted analysis of the primary endpoints and other dichotomous outcomes (e.g. complication rates). Time-to-failure analyses (Kaplan-Meier plots and logrank tests) will also be used in secondary analyses of the primary outcome as described above under "Interim Monitoring." Treatment comparisons will be adjusted for covariates with the logistic model for dichotomous endpoints and proportional hazards models for time-to-failure analyses. Analysis of continuous outcomes such as the quality of life subscales will be based on change from baseline. Prognostic models will be developed using baseline urodynamic testing results and other baseline covariates to explore the extent to which baseline measures can be used to predict surgical success. Time-to-event methods will be utilized to characterize time to normal voiding. In addition to comparing treatment groups with respect to satisfaction with surgery, the analysis of this outcome will include an evaluation of expectations of surgery as a predictor of satisfaction.

L. RECRUITMENT

To assess ability of the nine clinical centers to enroll the required number of patients (73 patients per center) into the trial over a two-year period, each center provided data in July 2001 regarding the number of Burch and sling procedures performed over the prior 12-months. These data are displayed in Table 2. Based on these data and the estimated enrollment rate of 20% of eligible patients, there appear to be a sufficient pool of patients from which to recruit. In the event that the enrollment rate has been overestimated (i.e. fewer patients agree to participate in the trial), several additional sources of potential patients have been identified:

- Investigator's office (might include patients of a non-study surgeon in a group practice);
- Referrals from colleagues;
- Post-card announcements in clinical areas/offices;
- Advertising: newspapers; newsletters; cable TV or public service announcements; websites of professional organizations, advocacy groups, or NIH; health fairs, health clubs, billboards;
- Mailings to enriched lists, e.g., former patients.

Table 2. Number of Procedures by Site: Approximate 12 Months prior to July 2001

Site	Burch	Sling
University of Alabama - Birmingham	68	162
University of California - San Diego	123	152
University of Maryland	46	155
University of Pittsburgh	33	297
University of Texas - Dallas	141	102

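### A completer Fisher test keeps early failures and loses unfailed women who skip the 24-month tests; inflating 260 to 325 per arm restores precision but leaves the success rates biased downward

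*Protocol*

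**What the plan says.** Protocol section D makes success conditional on every component: pad test, diary, MESA stress items, stress test and no retreatment. Failure needs only one positive component at 6 months or later, or retreatment at any time. It is permanent: "Once a woman is documented as a treatment failure, she cannot be classified as a success for that endpoint at later time points". Section K.1 adds that failure can be documented before 24 months, whereas success cannot be fully documented until then.

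K.1 sizes the trial at 260 women per arm (520 in all), a number meant to "ensure 80% power to detect a 12 percentage point difference (60% vs. 72%) using a two-sided" test, which is Fisher's exact test at 0.05. It then says: "In order to meet the criteria for success, patients must be willing to undergo a fairly intensive measurement process", and expects that "It seems likely that some women who consider themselves to be cured will not comply with this regimen". The response is: "Therefore, to adjust for a 20% non-compliance rate, the target sample size will be inflated to 325 per group, or 650 total".

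Section K.3 states that Fisher's "exact test will be used for unadjusted analysis of the primary endpoints", and gives no denominator. Kaplan-Meier and logrank analyses of the primary outcome are planned as secondary.

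**The concern.** A woman who has already failed stays classified whether or not she attends at 24 months. Sections H.5 and I.3 also bring her 24-month battery forward to the time of failure. A woman who has not failed and skips the battery is neither a success nor a failure. Missing 24-month data can therefore remove only women who have not yet failed, and K.1 itself expects some of them to be women who feel cured.

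K.1 treats this as a loss of numbers. A larger sample makes up for lost precision, but it does not put the missing successes back into the proportion. At stake are the 24-month success rate in each arm and the risk difference on which the trial is powered. If skipping differs between arms, the treatment comparison is also at stake.

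**Working it through.** **The plan's own figures.** Inputs from K.1: 60% vs 72%, two-sided 0.05, Fisher's exact test, 20% non-compliance.
- The normal-approximation sample size with continuity correction is 260 per arm. Full enumeration of Fisher's test at 260 per arm gives power 0.800.
- 260 / (1 − 0.20) = 325. The arithmetic is right, and it ties the stated power to about 260 evaluable women per arm.

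**Assumptions for illustration.** The documents give only the 20% total, not who skips or when failures occur. True success is taken as 66% (midpoint of 60% and 72%), with 25% failed by 12 months and 34% by 24 months.

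**Random skipping.** Let 20% of women unfailed at 12 months skip the 24-month battery, whatever their result would have been.
- Observed successes: 0.66 × 0.8 = 0.528.
- Observed failures: 0.25 + 0.09 × 0.8 = 0.322.
- Completer success rate: 0.528 / (0.528 + 0.322) = 62.1%.
- Kaplan-Meier: 0.75 × (1 − 0.072/0.60) = 66%, so it is unbiased here.

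**All skippers are successes, 20% of the arm.**
- Completers: (0.66 − 0.20) / 0.80 = 57.5%.
- Kaplan-Meier: 0.75 × (1 − 0.09/0.55) = 62.7%, which is better but still low.

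**Range over the early-failure assumption.** Suppose 20% of the arm skips, at random among women unfailed before 24 months. Completers then show 64.5%, 62.6% or 60.4% when 25%, 50% or 75% of failures are documented before 24 months.

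**Equal skipping in both arms.**
- At a common 66%, exact Fisher rejection is 0.040 both under random skipping (62.1%, about 276 per arm) and under success-only skipping (57.5%, 260 per arm).
- With 60% vs 72% true and the same fraction of successes skipping in each arm (0.20/0.66 = 30.3%), completers show 51.1% vs 64.2%. The difference is 13.1 points instead of 12, the odds ratio is unchanged at 1.714, and power is 0.84.

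**Unequal skipping, no true difference (66% in both arms, only successes skip; percentages of each arm).**

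| Skipping | Completers | Evaluable n | False difference | Exact rejection |
|---|---|---|---|---|
| 17.5% vs 22.5% | 58.8% vs 56.1% | 268, 252 | 2.7 points | 0.085 |
| 15% vs 25% | 60.0% vs 54.7% | 276, 244 | 5.3 points | 0.21 |

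For 15% vs 25%, Kaplan-Meier gives 0.75 × (1 − 0.09/0.60) = 63.75% against 0.75 × (1 − 0.09/0.50) = 61.5%. The false difference shrinks to 2.25 points but does not vanish.

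**Unequal skipping, true 60% vs 72%.**
- Skipping of 15% vs 25% (more in the better arm): 52.9% vs 62.7%, power 0.59.
- The reverse, 25% vs 15%: 46.7% vs 67.1%, rejection above 0.99 through an exaggerated difference.

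**Alternative reading: skippers counted as non-successes, 325 per arm.**
- 20% of successes skip: 0.60 × 0.8 = 48% vs 0.72 × 0.8 = 57.6%, power 0.67.
- 20% of each arm skips, all successes: 40% vs 52%, power 0.86.

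**The case against.** The strongest reply is that the protocol never says unfailed, unassessed women are left out of the Fisher test. That rule commonly belongs in a statistical analysis plan, which is not at hand. This stands as a limit: exclusion is inferred from 260/0.8 = 325. It does not dispose of the point, because K.1 does state a mechanism linked to outcome and answers it with sample size alone.

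Three stronger readings are tempting, and the documents do not support them.
- *The primary test is invalid.* With the same skip rate among successes in both arms, the level holds and the odds ratio is preserved. A false effect needs arm-specific skipping. Patients are blinded only until after the operation (section F), so this is possible, but nothing shows it. The 15% vs 25% pattern is an assumption.
- *Non-compliers are mainly the cured.* K.1 says only that some women who think themselves cured will skip. Feeling cured is also not the same as meeting the section D criteria. The 57.5% figure is an extreme case.
- *Counting skippers as non-successes must cost the stated power.* That depends on the pattern: 0.67 in one case, 0.86 in another.

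It is also fair to say that time-to-failure analyses are already planned, and that Kaplan-Meier does not remove informative loss. Both are accepted, and the second is why the fix goes beyond Kaplan-Meier.

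**Conclusion.** The point holds as a bias in the 24-month success rates and the risk difference under the completer analysis that K.1 implies. Under the stated assumptions the understatement is about 4 points with random skipping (66% to 62.1%) and 8.5 points if 20% of the arm skips and all are successes. Varying the share of early failures from 25% to 75% gives about 1.5 to 5.6 points when skipping is unrelated to the 24-month result.

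Bias in the comparison is conditional on skipping that differs by arm. A 5-point gap would roughly double the error rate (0.040 to 0.085), and a 10-point gap would raise it to 0.21. The sample size arithmetic itself is correct.

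All these figures concern the overall endpoint. The SUI-specific endpoint needs no diary or pad test, so it should be less affected.

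**What to change.** In K.1 and K.3, base the primary 24-month comparison on all randomised women. Either of two routes would do:
- estimate the 24-month failure-free proportion per arm with the time-to-failure methods already planned, censoring unfailed women at their last complete assessment; or
- impute 24-month status from the earlier visits.

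Keep Fisher's test on completers as a supporting analysis, and state how an unfailed woman without a complete 24-month battery is classified in it.

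Because skipping may be informative and Kaplan-Meier only reduces the bias, add by-arm bounds (all unclassified women successes, all failures) or sensitivity analyses that let missingness differ by arm. Collect the 24-month MESA and retreatment items by mail or telephone from women who decline the visit. That route is already used at 3 and 18 months.

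The cost is revised wording, slightly more analysis work, a fallback contact that uses existing procedures, and a headline test that is no longer exact.

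### K.1 sizes overall success on an unadjusted Fisher test, and K.3 neither makes its adjusted comparison primary nor names baseline urge severity, the factor K.1 blames for lower success

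*Protocol*

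**What the plan says.** **Sizing (K.1).** "A sample size of 260 per group, or 520 total, would" give the stated power, described as enough to "ensure 80% power to detect a 12 percentage point difference (60% vs. 72"%), with a two-sided Fisher's exact test at the 5% level. Then, "to adjust for a 20% non-compliance rate, the target sample size will be inflated to 325 per group".

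**Reason for the assumed rates (K.1, echoing section D).** Neither operation is expected to improve the urge component, so "the requirement of negative self-report and negative pad test may prevent women from achieving the clinical endpoint of" overall success even where the stress component is cured. K.1 draws the consequence from published rates of about 80 to 85%: "we expect to observe lower success rates in this trial, by approximately 15-20 percentage points".

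**Analysis (K.3).** Fisher's "exact test will be used for unadjusted analysis of the primary endpoints and other dichotomous outcomes". Shortly afterwards K.3 says that treatment comparisons of dichotomous endpoints will be adjusted in a logistic model. It lists no covariates and does not rank the two analyses.

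**Data available.** E.1 makes eligibility depend on "MESA stress symptom score (percent of total possible stress score) greater than MESA urge symptom score (percent of total possible urge score"), so every randomised woman has a baseline urge score. Appendix A schedules the MESA questionnaire at baseline, and H.3 lists it among the independent variables. Section F stratifies randomisation by clinical site only.

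**The concern.** The protocol names a baseline characteristic that it expects to influence overall success, measures it in every woman, and sizes the comparison on a test that does not use it. The adjusted analysis that would use it is planned, but it is neither designated primary nor tied to that characteristic.

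Two things are at stake. One is precision: outcome variation explained by baseline urge stays in the error of the unadjusted comparison, so a true 12-point difference is somewhat easier to miss. The other is clarity about the headline result. If the arms differ by chance in urge severity, which the randomisation does not balance, the adjusted and unadjusted results may disagree, and K.3 does not say which one decides.

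**Working it through.** **1. The plan's own figure.** Inputs from K.1: 60% vs 72%, two-sided 0.05, 260 per arm. The two-proportion formula with continuity correction gives 260 per arm (244 without it). Full enumeration of Fisher's test at 260 per arm gives power 0.800. Inflation gives 260/0.80 = 325. All of K.1's figures for this endpoint reproduce.

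**2. What Fisher's conservatism costs.** At 260 per arm without any covariate, power is 0.820 (logistic Wald), 0.825 (chi-square) and 0.829 (unpooled z-test), against 0.800 for Fisher. That is 2 to 3 points unrelated to urge. In simulations of 4,000 trials each, type I error was 0.036 to 0.045 for Fisher and 0.045 to 0.051 for the adjusted logistic model.

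**3. What the covariate adds if mixed incontinence is measured perfectly.** From K.1: success without an urge component s0 = 0.80 to 0.85, and a loss d = 0.15 to 0.20, so overall success is s0 − d. Assumed, because the protocol gives no figure: a share m of women with mixed incontinence.

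- Success in mixed women: q = s0 − d/m
- Variance explained: R² = m(1 − m)(s0 − q)² / [overall × (1 − overall)]
- SE = √(0.60×0.40/260 + 0.72×0.28/260) = 0.0412
- Adjusted power = Φ(0.12 / (SE × √(1 − R²)) − 1.96)

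Example with m = 0.50, s0 = 0.80, d = 0.15: q = 0.50 and R² = 0.25 × 0.30² / (0.65 × 0.35) = 0.099. Power = Φ(2.912/0.949 − 1.96) = Φ(1.107) = 0.866, which is 3.7 points above 0.829.

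**4. What it adds if the score is an imperfect proxy.** H.1c reports 87% agreement between the MESA questions and a clinician's assessment. As an illustration, take 0.87 as both sensitivity and specificity of a binary proxy. The share classed as mixed is p = 0.87m + 0.13(1 − m), and R² shrinks by the factor 0.74² × m(1 − m) / [p(1 − p)], which is about 0.50 to 0.55 here.

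| Assumed m | R², perfect | Gain over 0.829 | R², proxy | Gain over 0.829 |
|---|---|---|---|---|
| 40% | 0.15–0.26 | 5.5–9.5 points | 0.08–0.14 | 3.0–5.2 points |
| 50% | 0.10–0.18 | 3.7–6.5 points | 0.05–0.10 | 2.0–3.6 points |
| 60% | 0.07–0.12 | 2.4–4.3 points | 0.04–0.06 | 1.3–2.3 points |
| 70% | 0.04–0.08 | 1.6–2.8 points | 0.02–0.04 | 0.8–1.4 points |

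**5. Cross-check by a second method.** A logistic model, with the marginal rates held at 60% and 72% and a binary urge covariate carrying the same 15 to 20 point loss, gives power 0.844 to 0.912 for m = 40 to 60%. That is 2.4 to 9.2 points above the unadjusted logistic 0.820. With a continuous score, assumed odds ratios of 1.5, 2 and 3 per standard deviation give 0.833, 0.853 and 0.887, or 1.3, 3.3 and 6.7 points.

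**6. If all 325 per arm were evaluable.** Fisher power is 0.886 and the unadjusted logistic 0.896. A continuous score with odds ratios of 1.5 to 6 per standard deviation gives 0.905 to 0.974, which is 2 to 9 points above Fisher.

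**The case against.** The strongest reply is that adjustment is already planned. K.3 says without condition that treatment comparisons will be adjusted, and the analyses it labels secondary are the time-to-failure ones, not the logistic model. A reader might infer that the trial throws away all the power a covariate could give, or that a chance imbalance in urge would go uncorrected. The text does not support either reading, because it never places the adjusted model below Fisher's test.

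A reader might also put the loss from ignoring urge at 5 to 14 points. That range compares an adjusted test with Fisher's, so 2 to 3 points of it belong to the change of test. Its upper end needs a mixed share near 30%, which at the midpoint inputs (s0 = 0.825, d = 0.175) implies success of only 0.825 − 0.175/0.30 = 24% in mixed women. K.1 says only that urge may stand in the way of success. The published 80 to 85% is moreover an average from a heterogeneous literature, not a rate in women without urge.

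Other features could weaken the link further. Eligibility requires the stress score to exceed the urge score, which limits the range of the latter. G.7 leaves treatment of urgency after surgery to the physician.

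Finally, listing covariates is commonly left to a statistical analysis plan, and sizing on an unadjusted test is conservative. Both points are fair, and the absence of a covariate list alone would be no finding. What stands is narrower. The protocol itself chooses the sizing test and leaves open which analysis is primary, while naming the prognostic factor that would make the adjusted one the better choice.

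**Conclusion.** The point holds as an efficiency and clarity improvement, not as an error in the sample size. The 260 per arm, the 80% power and the 325 after inflation are all correct.

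At 260 evaluable women per arm, the covariate alone adds roughly 1 to 5 points of power with an imperfect score and about 2 to 9 points with perfect measurement. Leaving the conservative Fisher test adds about 2 to 3 points more. These ranges rest on an assumed mixed share of 40 to 70%, on reading K.1's 15 to 20 point reduction as wholly due to urge, and, for the lower range, on treating 87% agreement as both sensitivity and specificity. The protocol gives neither the share of mixed incontinence nor the strength of the link between urge and outcome, so the true gain could lie outside them.

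A reader might extend the argument to SUI-specific success. The document gives no basis for that: K.1's reasoning concerns the diary and pad-test requirements, which that endpoint omits.

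**What to change.** In K.3, state that the primary comparison of overall treatment success is the covariate-adjusted one, with baseline MESA urge score as a covariate fixed before outcomes are compared by arm. Report a standardised risk difference with a robust standard error from the logistic model. Keep Fisher's test as the supporting unadjusted analysis. Leave the sample size and its stated power as they are.

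Adjusting SUI-specific success for the baseline MESA stress score is optional.

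The cost is wording in the protocol or analysis plan, since the score already exists for every randomised woman. The small downside is a model-based estimate in place of a 2×2 table; reporting it as a risk difference keeps it readable.

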*Patient can be deferred for enrollment until respective time interval has been met.

E.2 Exclusion Criteria

1. Age < 21 years
2. Non-ambulatory (Ambulatory with assistive devices does not exclude the patient.)
3. Pregnancy by self-report or positive pregnancy test, or self-reported intention to become pregnant in the next 24-months
4. Current cancer chemotherapy or radiation therapy
5. Systemic disease known to affect bladder function (i.e., Parkinson's disease, multiple sclerosis, spina bifida, spinal cord injury or trauma)
6. Urethral diverticulum, current or previous (i.e. repaired)
7. Prior augmentation cystoplasty or artificial sphincter
8. < 12 months post-partum*[†]

9. Recent pelvic surgery (e.g. vaginal hysterectomy), i.e., endoscopic pelvic surgery <6 weeks or open pelvic surgery <6 months*
10. Participation in another treatment intervention trial that might influence the results of this trial.

*Patient can be deferred for enrollment until respective time interval has been met.

†“Partum” is defined as a delivery or other termination that occurs after 20 weeks.

If more than 6-months transpires between determination of eligibility and surgery, specified measures must be repeated to ensure current eligibility for the trial as well as to obtain current baseline values for critical measures that are subject to change. (See Section H.5 and Appendix A.)

F. RANDOMIZATION

Patients will be randomized in the operating room. It is recognized that there are disadvantages to this strategy, including the following points:

- Patients must agree to be blinded to the type of surgery they will get until after the operation;
- The surgeon(s) must be prepared to perform either type of procedure;
- The anesthesiologist must be willing and able to evaluate the patient without knowing which procedure will be performed.

The process of obtaining the randomized treatment assignment will be accomplished via a telephone call to an automated randomization system at the Biostatistical Coordinating Center (New England Research Institutes) from a touchtone telephone. A back-up hard copy of the assignment kept in a sealed envelope will be made available in the case of technical problems. Randomization will be stratified by clinical site, using permuted blocks.

G. TREATMENTS

G.1 Operative Procedures

The two procedures included in this trial are the Burch modified Tanagho procedure and the autologous fascia sling procedure.

G.2 Standardization of Operative Procedures

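### Randomisation is stratified by site but the primary endpoints are tested with an unstratified Fisher's exact test: valid and powered as stated, though a site-stratified test would be modestly more efficient

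*Protocol*

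**What the plan says.** **Randomisation (Protocol, section F).** "Randomization will be stratified by clinical site, using permuted blocks". No other stratification factor is named. Section L gives nine centres and 73 patients per centre.

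**Sizing (section K.1).** The calculation is for 260 per group (520 total), and the purpose given for that number is to "ensure 80% power to detect a 12 percentage point difference (60% vs. 72" per cent. The sizing is tied to a named test and level: "using a two-sided $\alpha=.05$ Fisher's exact test". The allowance for incomplete assessment comes next: "to adjust for a 20% non-compliance rate, the target sample size will be inflated to 325 per group, or 650 total". The SUI-specific endpoint has its own power statement: "The target sample size will ensure >85% power for detecting a 10 percentage point difference (80% vs. 90" per cent.

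**Analysis (section K.3).** Fisher's "exact test will be used for unadjusted analysis of the primary endpoints and other dichotomous outcomes". The same paragraph adds: "Treatment comparisons will be adjusted for covariates with the logistic model for dichotomous endpoints", with proportional hazards models for time to failure. It does not list the covariates, does not mention site, and does not say that the adjusted comparison is the primary one. The logrank tests in K.2 and K.3 are described without stratification.

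**The concern.** When randomisation is blocked within sites, the arms are balanced on site by design. A test that ignores site then uses a variance that includes between-site differences which cannot contribute to the treatment contrast. Such a test stays valid but becomes conservative if success rates differ between sites. Fisher's test adds its own conservatism from discreteness. Both effects leave power unused that the trial could have from data it already collects. Section B.4 mentions different patient populations and referral patterns across centres, and Appendix B asks the DSMB to look at outcomes by surgeon and site, so differences between sites are at least contemplated.

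**Working it through.** **Inputs from the Protocol.** Success rates 60% and 72%, two-sided alpha 0.05, 260 per group before inflation, 20% non-compliance, 80% vs 90% for the SUI-specific endpoint (all K.1); nine sites (L).

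**Input that is assumed.** The spread of success rates between sites, which the Protocol does not give. It is taken as the SD of the site log-odds, from 0 to 1.0, with (near-)equal site sizes, exact within-site balance and a common odds ratio.

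**Step 1: reproduce the stated figure.** The uncorrected formula is

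n = [1.96·√(2·0.66·0.34) + 0.8416·√(0.60·0.40 + 0.72·0.28)]² / 0.12² = (1.313 + 0.559)² / 0.0144 ≈ 243.4, so 244 per group.

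With the continuity correction, which approximates Fisher's test:

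n' = (243.4/4)·[1 + √(1 + 4/(243.4·0.12))]² ≈ 259.8, so 260 per group.

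Inflation: 260/0.80 = 325. Exact enumeration of Fisher's test at 260 per group gives power 0.8001. For 80% vs 90% it gives 0.874 at 260 per group and 0.939 at 325, consistent with the stated figure of more than 85%. The plan's figures are right.

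**Step 2: the cost of the exact test when sites are alike (exact enumeration, 260 per group).**

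| Test | Size at 66% in both arms | Power, 60% vs 72% | Power, 80% vs 90% |
|---|---|---|---|
| Fisher | 0.040 | 0.800 | 0.874 |
| Chi-square, uncorrected | 0.050 | 0.826 | 0.900 |

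The cost is 2.6 points of power on each endpoint. In patients it is 260 − 244 = 16 per group. After inflation this is 325 − 244/0.80 = 325 − 305 = 20 per group, or 40 in total.

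**Step 3: add site stratification.** For site i with n_i per arm, N_i = 2n_i, m_i successes in total and x_i in one arm:

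E_i = m_i/2, V_i = m_i(N_i − m_i)n_i² / [N_i²(N_i − 1)], z = |Σ(x_i − E_i)| / √ΣV_i.

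The test rejects when z ≥ 1.96. The continuity-corrected version subtracts 0.5 from the numerator. Simulation used 100,000 trials per setting at 260 per group, with marginal rates held at 60% and 72% for power and at 66% in both arms for size. The Monte Carlo standard error of power is about √(0.83·0.17/100,000) = 0.12 points.

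| SD of site log-odds | Site range, 60% arm | Fisher | Chi-square | CMH, uncorrected | CMH, corrected | Size: Fisher | Size: CMH, uncorrected |
|---|---|---|---|---|---|---|---|
| 0 | 60% | 80.0% | 82.6% | 82.5% | 80.0% | 3.9% | 4.8% |
| 0.25 | 50–70% | 80.1% | 82.8% | 83.1% | 80.5% | 3.9% | 4.9% |
| 0.5 | 40–78% | 80.5% | 83.2% | 84.5% | 82.1% | 3.5% | 5.1% |
| 0.75 | 31–85% | 81.3% | 83.9% | 86.5% | 84.2% | 2.9% | 4.9% |
| 1.0 | 23–90% | 82.3% | 84.9% | 88.9% | 86.8% | 2.3% | 4.9% |

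**Step 4: separate the two sources.** The share due to stratification is uncorrected CMH minus uncorrected chi-square. From the unrounded results this is nil at SD 0, 83.09 − 82.79 = 0.3 points at SD 0.25, 84.51 − 83.15 = 1.4 at SD 0.5, 86.49 − 83.92 = 2.6 at SD 0.75 and 88.94 − 84.87 = 4.1 at SD 1.0. The share due to leaving the exact test is 2.6 to 2.7 points throughout. A continuity-corrected CMH test gains nothing over Fisher when sites are alike.

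**Step 5: if all 325 per group are evaluable.** Fisher has 88.4%, 88.6% and 89.3% power at SD 0, 0.25 and 0.5; uncorrected CMH has 89.9%, 90.3% and 91.4%. The gain shrinks to about 1.5 to 2 points. Fisher's size at SD 0.5 is 3.7%.

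The interim looks were not modelled, and the gain from stratifying the logrank tests was not computed.

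**The case against.** The strongest reply is that the plan is coherent. The same test is used for sizing and for analysis, its conservatism was paid for in the 260 per group, and type I error stays below 5%. This stands. A reader might infer that the trial is underpowered or the test invalid; step 1 rules out the first, and conservatism is not invalidity.

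A second reply is that K.3 already plans covariate-adjusted logistic and proportional hazards models. This also stands in part. A reader might infer that site is to be ignored altogether, but the text neither includes nor excludes it, and a covariate list is commonly left to the SAP. What remains is that the one test named and powered for the primary endpoints does not use the stratification factor, and nothing makes the adjusted comparison primary.

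Third, the procedure counts by centre in Table 2 (for example 636 Burch and 65 sling at one centre, 33 and 297 at another) might be read as proof that success rates differ by site. They are counts collected for recruitment feasibility, not outcomes. Sections G.2 and O standardise the procedures and certify surgeons, which would tend to limit spread. If uneven experience with the two operations did matter, it could appear as treatment-by-site interaction, which the common-odds-ratio simulation does not represent.

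Finally, the change is not free. An exact guarantee on type I error is replaced by a large-sample one, although simulated size stayed at 4.8% to 5.1% with nine sites. Logistic regression estimates a conditional odds ratio, not the marginal contrast of 60% with 72%. Nor can it be said that the plan's standard errors are too wide: Fisher's test yields none, and the Protocol fixes no interval method.

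**Conclusion.** The point holds as a minor efficiency improvement and not as an error in the stated power. Against Fisher at 260 per group, an uncorrected site-stratified CMH test gains about 2.5 points if sites are alike and about 4 points at an assumed site log-odds SD of 0.5. Up to that spread, most of the gain comes from leaving the exact test. Gains of 5 to 7 points need site success rates in the 60% arm spanning about 31% to 85% or wider, which nothing in the Protocol establishes. For the SUI-specific endpoint the gain with sites alike is 2.6 points (step 2); the effect of site spread on that endpoint is not tabulated here. The results rest on near-equal sites, exact within-site balance, a common odds ratio and no allowance for interim looks.

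**What to change.** In K.3, name one primary comparison for both primary endpoints: either the CMH test stratified by the nine sites, stated to be without continuity correction, or the already planned logistic model with site included. Report a site-adjusted risk difference with its 95% confidence interval alongside. Stratify the logrank tests by site, including the interim ones in K.2. Keep Fisher's test for rare complications, where large-sample tests are least reliable.

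The sample size can stay as it is; K.1 would then be slightly conservative for the named test. The change costs a few sentences and needs no further patients or data. Its one statistical price is the loss of the exact type I error guarantee. It should be made before outcomes are compared by arm.
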